7.1. Summary of Study Design

[...]

[figure not shown]
This study (Study AACD) will enroll patients with MCI due to AD, mild AD, or moderate AD with amyloid deposition confirmed by florbetapir PET imaging using National Institute on Aging-Alzheimer's Association (NIAAA) work group consensus guidelines (Albert et al. 2011; McKhann et al. 2011). This study will be conducted at sites in multiple countries, including the United States and Japan. Up to 150 patients may be enrolled to ensure so that approximately 72 patients (7 dosing cohorts of 8 to 12 patients) complete the study.

Previous diagram:

[figure not shown]
Part A: Single dose; 72-week follow-up

Part B: 24-weeks, Q2W multiple dose treatment; 48-week follow-up

[figure not shown]

Part C: Chronic dose, 72-week, Q4W multiple dose treatment; 12-week follow-up

[figure not shown]

Revised diagram:

[figure not shown]
Part A: Single dose; 72-week follow-up (Cohorts 1 & 2), 24-week follow-up (Cohort 3)

Part B: 24-weeks, Q2W multiple dose treatment; 48-week follow-up

Part C: Chronic dose, 72-week, Q4W multiple dose treatment; 12-week follow-up

Cohort 2 will only be initiated after review of safety data from Cohort 1. Thereafter, Cohort 3 will be initiated after review of safety data from Cohort 2. Cohorts 4 and 5 will be initiated after review of safety and PK data from their respective single-dose cohorts. An additional requirement for Cohort 5 is confirmation that at least 2 patients have received at least 3 doses each of LY3002813 safely in Cohort 4. Cohort 6 and Cohort 7 may proceed in parallel with Cohorts 4 and 5, respectively. In addition, Cohort 7 will only be initiated after confirmation that at least 2 patients have received at least 2 doses each of LY3002813 safely in Cohort 6. Safety/PK reviews will occur after a minimum of 4 patients receiving LY3002813 and 1 patient

receiving placebo have been dosed. For Cohorts 1 to 3, no more than 1 patient will be dosed on any one particular day. For Cohorts 4 to 7, patients dosed on the same day at any one site should not be dosed simultaneously but should be separated by at least 1 hour. Each cohort will contain ~~a minimum of approximately 6~~ (single dose) or 9 (multiple dose) patients treated with LY3002813 and 2 to 3 patients treated with placebo so that the study can detect target engagement and ADA frequency relative to those observed in Study AACC.

7.1.3. Part A: Single Dose Cohorts (Cohorts 1 through 3)

Safety, PK, and PD will be assessed in Cohorts 1 through 3 after single doses of LY3002813 or placebo. The planned doses are 10, 20, and 40 mg/kg IV for Cohorts 1, 2, and 3, respectively; with ~~a minimum of~~ 8 patients (6 LY3002813; 2 placebo) ~~completing~~ ~~planned to be enrolled in~~ each cohort. Dose escalation will only occur after the safety from the preceding cohort has been established in at least 4 patients receiving LY3002813 and 1 receiving placebo. Safety data will be collected at least 1 week after dosing for dose escalation to Cohort 2 and at least 4 weeks after dosing for dose escalation to Cohort 3. Enrollment in Cohorts 2 and 3 will only commence once enrollment into the preceding cohort has completed. Safety, PK, and PD will be assessed at regular intervals for approximately 72 weeks (in Cohorts 1 and 2) or 24 weeks (in Cohort 3) after starting the dosing with study drug (Attachment 1).

7.1.4. Part B: 24-Week Q2W Multiple Dose Cohorts (Cohorts 4 through 5)

Safety, PK, and PD will be assessed in Cohorts 4 and 5, during and after multiple doses of LY3002813 or placebo have been administered Q2W for 24 weeks. The planned doses are 10 and 20 mg/kg IV with ~~a minimum of~~ 12 patients (9 LY3002813; 3 placebo) ~~completing~~ ~~planned to be enrolled in~~ each cohort. Cohort 4 (10 mg/kg IV Q2W for 24 weeks) will be initiated after review of the safety (at least 1 week after dosing) and PK data (complete Day 29 visit) from at least 4 patients receiving LY3002813 and 1 receiving placebo in Cohort 1. Cohort 5 (20 mg/kg IV Q2W for 24 weeks) will only be initiated after review of the safety and PK data (at least 4 weeks after dosing) from Cohort 2 in at least 4 patients receiving LY3002813 and 1 receiving placebo, and after confirmation that at least 2 patients have been dosed safely with LY3002813 at least 3 times each in Cohort 4. Safety and PD will be assessed at regular intervals for approximately 48 weeks after completion of 24 weeks of dosing with LY3002813 (Attachment 1).

7.1.5. Part C: Chronic, 72-Week Q4W Multiple Dose Cohorts (Cohorts 6 and 7)

Safety, PK, and PD will be assessed in Cohorts 6 and 7 during and after multiple doses of LY3002813 or placebo have been administered Q4W for up to 72 weeks, or when the LY3002813-induced reduction in amyloid measured by florbetapir reaches the maximum reduction (defined as SUVr <1.1 for 2 consecutive scans) (Joshi et al. 2015). The planned doses

are 10 and 20 mg/kg IV with a minimum of 12 patients (9 LY3002813; 3 placebo) planned to be enrolled in completing each cohort. Cohort 6 (10 mg/kg IV Q4W) and Cohort 7 (20 mg/kg IV Q4W) may proceed, in parallel with Cohorts 4 and 5, respectively. In addition, Cohort 7 will only be initiated after confirmation that at least 2 patients have received at least 2 doses each of LY3002813 safely in Cohort 6. The maximum dose of 20 mg/kg will not be exceeded. If a patient is deemed to be amyloid negative by florbetapir PET before completion of 18 months' dosing (SUV_r <1.1 for 2 consecutive scans), the patient will receive placebo infusion for all subsequent visits and continue the Part C visit schedule, including assessment of sustained amyloid reduction at the scheduled PET scan assessments. Safety, PK, and PD will be assessed for all patients at regular intervals for approximately 12 weeks after completion of 72 weeks of dosing with LY3002813 (Attachment 1).

7.1.7. Study Design for Japanese Patients

Sites in Japan will participate in this study to recruit Japanese patients.

At least 2 Japanese patients should be enrolled in each dose cohort for Cohorts 1, 2, 4, and 6. Assuming that the cohorts will be dosed based on safety reviews, it is intended that at least 3 Japanese patients will be enrolled in each dose cohort for Cohorts 3, 5, and 7; however, recruitment to a cohort will not be contingent upon fulfilling these requirements. At least 17 Japanese patients should be enrolled in the study when all cohorts are dosed. Japanese patient enrollment into cohorts should ensure sufficient exposures at applicable doses to support future studies (for example, at least 6 Japanese patients overall exposed to LY3002813, and at least 2 Japanese patients per cohort exposed to LY3002813 at the highest doses to be used in future studies). For the purpose of safety evaluation in Japanese patients during the study, Japanese patients at sites in Japan and up to third-generation Japanese patients at sites outside of Japan will be included. The definition of up-to-third-generation Japanese is defined in Section 8.1.

9.2.3. 18F-AV-1451 Dosage and Administration

A total of two 18F-AV-1451 PET scans will be performed approximately 72 weeks apart, except for Cohort 3 where scans will be approximately 24 hours apart. During this study, patients will receive a single IV administration of approximately 240 MBq (6.5 mCi) of 18F-AV-1451. At approximately 75 minutes following injection, a continuous 30 minute brain scan (6 acquisitions, each of 5 minutes in duration) will be performed.

Previously conducted 18F-AV-1451 PET scans can be used as baseline measurements, if the sponsor approves. During these previous scans, patients might receive a single IV administration of approximately 240 MBq (6.5 mCi) or 370 MBq (10.0 mCi) of 18F-AV-1451. For each patient, the baseline data originally collected for previous Lilly and Avid Radiopharmaceuticals studies can only be entered/sent for Study AACD after the patient signs the ICF agreeing to participate in this study.

9.2.4. Radiation Doses Associated with PET Imaging

[...]

In a previously conducted and accepted 18F-AV-1451 scan, the patient might have been administered with 370 MBq (10.0 mCi) rather than 240 MBq (6.5 mCi) of 18F-AV-1451. In this case, the patient would be exposed to an additional 2.9 mSv of ionizing radiation.

10.5.2. Imaging

A total of two 18F-AV-1451 PET scans will be performed, approximately 72 weeks apart, except for Cohort 3 where scans will be approximately 24 weeks apart. 18F-AV-1451 PET scan should be performed at least 24 hours apart from the florbetapir scan (for further details on florbetapir imaging see Section 9). The change in grey matter SUV_r will be compared to total dose exposure. Additional approaches for tau PET quantitation may be applied based on emerging data.

MRI changes in brain volume over the course of the study will be explored. Over an approximate span of 72 weeks, except for Cohort 3, which will be 24 weeks, screening MRI and up to 8 post-baseline MRIs will be performed, mostly for safety monitoring (ie, occurring 4 weeks after the first dose, every 12 weeks starting from the first dose, and up to 12 weeks after the last dose). However, additional MRI scans are included for exploratory evaluation of brain structural changes (including, but not limited to, whole brain, ventricle, and hippocampal volumes), white matter and tissue microstructure changes, and functional connectivity in brain networks at baseline, 24 weeks, 48 weeks, and 72 weeks as applicable.

11.1. Determination of Sample Size

Up to approximately 150 patients may be enrolled ~~to ensure~~ so that approximately 72 patients complete the study. Cohorts 1, 2, and 3 are each planned to have ~~a minimum of approximately~~ 8 patients (6 LY3002813; 2 placebo) complete the study. Cohorts 4 and 5 are each planned to have ~~a minimum of approximately~~ 12 patients (9 LY3002813; 3 placebo) complete the study. Also, Cohorts 6 and 7 are each planned to have ~~a minimum of approximately~~ 12 patients (9 LY3002813; 3 placebo) complete the study.

Attachment 1. Protocol AACD Study Schedule*New Schedule of Activities for Cohort 3:***Schedule of Activities, Protocol I5T-MC-AACD, Part A: Cohort 3 (Single Dose), Visit 4 through Visit 13**

Procedure												
Visit No.:	V4 ^a	V5 ^b	V6	V7	V8	V9	V10	V11	V12	V13	ED	
Day Relative to First Dose	-4	1	4	6	8	15	29	57	85	169		
Week			1	1	1	2	4	8	12	24		
Tolerance Interval for Visit (days)	±4*	0	0	±1	±4	±4	±4	±4	±4	±7		
Entry and Administrative/Every Visit												
Body weight	X						X		X	X		
Previous/concomitant medications	X	X	X	X	X	X	X	X	X	X		
Preexisting conditions/AEs		X	X	X	X	X	X	X	X	X		
Study medication administered ^l		X										
Cognitive Assessments												
ADAS-Cog	X									X	X	
ADCS-MCI-ADL24	X									X	X	
NTB	X									X	X	
CDR										X	X	
FCSRT-IR										X	X	
MMSE										X	X	
Safety Assessment												
Vital signs	X	X ^m	72h	X	X	X	X	X	X	X	X	
C-SSRS ^d /SHSF ^f	X	X				X	X	X	X	X	X	
Physical/neurological examination		X ^p				X	X	X	X	X	X	
12-lead digital ECG ^e	X ^m	X ^m	72h	X	X	X	X	X	X	X	X	
Imaging												
MRI ^{h,i}							X		X	X	X	
Florbetapir PET scan									X	X	X	
18F-AV-1451 PET scan	X ^x								X ⁱ	X ⁱ		
Laboratory Assessments												
LP ⁿ	X		X									
ABI tempus tube/blood RNA	X				X							
Pharmacogenetic sample ^o	X											
Clinical chemistry, electrolytes, hematology, urinalysis ^g		X		X	X	X	X	X	X	X	X	
Coagulation tests (at local laboratory, prior to LP, except the V6 LP) ^y	X											
Serum LY3002813 PK ^q		predose, end of infusion, 3, 24, 48h	72h	X	X	X	X	X	X	X	X	
Plasma A β	X		X									
Serum for immunogenicity ^s	X			X	X	X			X	X	X	
Aliquoted plasma (EDTA) and serum for storage	X			X								
Stored serum for possible exploratory immune safety laboratory tests ^t	X								X		X	

Attachment 3. Protocol AACD Blood Sampling Summary

New blood sampling table for Cohort 3:

Protocol I5T-MC-AACD Sampling Summary Part A (Cohort 3)

Purpose	Maximum Blood Volume per Sample (mL)	Maximum Number of Blood Samples	Maximum Total Volume (mL)
Screening tests^a	26	1	26
Clinical laboratory tests^a	12	9	108
Coagulation tests	6	1	6
Drug assays^b	4	13 (+3)	52 (12)
Blood discard for cannula patency	3	11	33
Immunogenicity assessments^a	10	6	60
Pharmacogenetic sample^c	11	1 (+1)	11 (11)
Nonpharmacogenetic/biomarker samples	21	2	42
Blood sample for exploratory immune safety	14	2	28
Total			366 (389)
Total for clinical purposes (rounded to the nearest 10 mL)			370 (390)

a Additional samples may be drawn if needed for safety purposes.

b A maximum of 3 blood samples per patient may be drawn at additional time points during the study, if warranted and agreed upon between both the investigator and sponsor.

c An additional sample may be taken postdose if required.

Leo Document ID = 0c1c3979-9ccc-49ad-98e9-3e059d8d90bf

Approver: PPD

Approval Date & Time: 14-Dec-2017 19:45:14 GMT

Signature meaning: Approved

Approver: PPD

Approval Date & Time: 14-Dec-2017 19:47:10 GMT

Signature meaning: Approved

**Revision History**

Statistical Analysis Plan (SAP) Version 1 was approved prior to first patient visit when a patient receives study drug.

### 3. Study Objectives

#### 3.1. Primary Objective

The primary objective is to assess the effect of LY3002813 on brain plaque load using florbetapir imaging.

#### 3.2. Secondary Objectives

The secondary objectives are to:

- further evaluate the safety and pharmacokinetics (PK) of single and multiple doses of LY3002813 in Japanese and non-Japanese patients with mild cognitive impairment (MCI) due to Alzheimer's disease (AD) or mild to moderate AD
- evaluate the immunogenicity of single and multiple doses of LY3002813.

#### 3.3. Exploratory Objectives

The exploratory objectives are to:

- assess the relationship among dosing regimens, PK, and pharmacodynamic (PD) from florbetapir scan, immunogenicity, and immune safety
- evaluate changes in plasma, serum, and cerebrospinal fluid (CSF) biomarkers following multiple doses of LY3002813
- evaluate the effects of single and multiple doses of LY3002813 on cognitive function
- evaluate changes in MRI measures and 18F-AV-1451 tau positron emission tomography (PET) scan
- evaluate genetic interactions with study treatment response or any adverse events (AEs).

#### 3.4. Summary of Study Design

This study (Study I5T-MC-AACD [AACD]) will enroll patients with MCI due to AD, mild AD, or moderate AD with amyloid deposition confirmed by amyloid PET imaging using the National Institute on Aging-Alzheimer's Association (NIAAA) work group consensus guidelines (Albert et al. 2011, McKhann et al. 2011). This study will be conducted in multicountry sites including the United States and Japan. Up to 150 patients may be enrolled to ensure that approximately 72 patients (7 dosing cohorts of 8-12 patients) complete the study.

The study will be conducted in at least 7 cohorts ([Figure AACD.3.1](#)):

- Cohort 1: 10 mg/kg intravenous (IV) single dose
- Cohort 2: 20 mg/kg IV single dose

- Cohort 3: 40 mg/kg IV single dose (initiated after the 4-week safety review of Cohort 2)
- Cohort 4: 10 mg/kg IV every 2 weeks (Q2W) for 24 weeks
- Cohort 5: 20 mg/kg IV Q2W for 24 weeks (initiated after the 4-week safety review of Cohort 2; dosing interval may be modified based on single-dose PK of 20 mg/kg LY3002813)
- Cohort 6: 10 mg/kg IV every 4 weeks (Q4W) for up to 72 weeks
- Cohort 7: 20 mg/kg IV Q4W for up to 72 weeks (initiated after the 4-week safety review of Cohort 2)

[figure not shown]
Cohorts 1, 2, 4, and 6 may be initiated in parallel. Cohorts 3, 5, and 7 can only be initiated after a review of safety data from a minimum of 4 patients on LY3002813 and 1 patient on placebo completing the 4-week safety review in Cohort 2. Each cohort will contain 6 to 9 patients treated with LY3002813 and 2 to 3 patients treated with placebo so that the study can detect target engagement and ADA frequency relative to those observed in Study I5T-MC-AACC (AACC).

The primary target engagement outcome is the reduction of cerebral amyloid as measured by quantitative amyloid PET imaging (SUVr) assessed at baseline and 12 weeks, 24 weeks, 36 weeks, 48 weeks, and 72 weeks after starting treatment. The early postbaseline scans aim to assess the time course of amyloid reduction; the later scans aim to assess sustainability of amyloid reduction after completion of dosing in Parts A and B, and maximal amyloid removal in Part C.

[figure not shown]
Safety and PK of LY3002813 will be assessed throughout the study for each Cohort. In addition, blood samples for the assessment of immunogenicity will be taken at regular intervals throughout the dosing and follow-up periods. For Cohorts 1, 2, and 3, a cerebrospinal fluid (CSF) sample will be taken by single lumbar puncture (LP) at baseline, another approximately 3 days after dosing to measure the CSF concentration of LY3002813 and CSF biomarkers. For Cohorts 4 to 7, a CSF sample will be taken by single LP at baseline and after 24 weeks dosing, or the last dose if treatment is stopped earlier.

As noted previously, a high prevalence of ADAs was observed in Study AACC; therefore, a risk management plan for immune safety is incorporated into the clinical trial. Other safety monitoring in Study AACD will include serial magnetic resonance imaging (MRIs) beginning at baseline and following according to the study schedule for assessment of amyloid-related imaging abnormalities, adverse events (AEs), electrocardiograms (ECGs), vital signs (blood pressure, heart rate), physical examinations, neurological examinations, and safety laboratory tests of blood (including immunogenicity) with approximately a 12-week follow-up safety visit after the final dose.

[figure not shown]
#### **Part A: Single dose; 4-week follow-up**

#### Part B: 24-weeks, Q2W multiple dose treatment; 48-week follow-up

**Part C: Chronic dose, 72-week, Q4W multiple dose treatment; 12-week follow-up**

Abbreviations: IV = intravenous; MRI = magnetic resonance imaging; PET = positron emission tomography; Q2W = every 2 weeks; Q4W = every 4 weeks; x = times.

Assessments: **A**, amyloid PET; **I**, immunogenicity; **M**, MRI; **T**, tau PET; **C**, cognition; **F**, cerebrospinal fluid; **D** – dosing; **S** - 4 week safety review of Cohort 2

\* - cohorts may be initiated after 4-week safety review of Cohort 2. In addition, for Cohort 5, confirmation that at least 2 patients have been dosed safely for at least 2 doses each in Cohort 4, will be required before commencing this cohort.

f/u – follow-up assessments (Immunogenicity, **I**: MRI, **M**) 12 weeks after last dose for Cohorts 6 and 7

NOTE: vertical lines indicate 4-week intervals. Additional immunogenicity assessments will be performed every 12 weeks if titers are increasing.

### Figure AACD.3.1. Study Design.

## 4. A Priori Statistical Methods

### 4.1. Determination of Sample Size

Up to approximately 150 patients may be enrolled to ensure that approximately 72 patients complete the study. Cohorts 1, 2, and 3 are each planned to have a minimum of 8 patients (6 LY3002813; 2 placebo) complete the study. Cohorts 4 and 5 are each planned to have a minimum of 12 patients (9 LY3002813; 3 placebo) complete the study. Also, Cohorts 6 and 7 are each planned to have a minimum of 12 patients (9 LY3002813; 3 placebo) complete the study.

The sample size is customary for studies evaluating safety, PK, and/or PD parameters; at the conclusion of the trial, confidence intervals (CIs) for PK, PD, and cognition endpoints may be computed in order to evaluate the precision of the estimates where appropriate. Based on prior Lilly clinical trials, 6 patients randomized to each LY3002813 dose and placebo provide over 90% power to detect at least a **CCI** mean SUVr reduction of a dose compared to that of placebo without multiple comparison adjustment. Based on Fixed and Adaptive Clinical Trial Simulator (FACTS) simulations, there is over 90% success rate that at least 1 LY3002813 dose separates from placebo with a success criterion of  $\Pr(\text{mean SUV}_r \text{ reduction of LY3002813 dose} < \text{mean SUV}_r \text{ reduction of placebo}) > \text{CCI}$ . If more patients are needed to determine safety, target engagement, PK, dosing, and/or race differences, then up to a total of 10 additional patients may be added.

In order to maintain a constant accrual rate, the randomization ratio will be 6:2 in Cohorts 1, 2, and 3; randomization will progress with a 9:3 ratio in Cohorts 4 to 7. It is intended that at least 2 Japanese patients will be enrolled in each dose cohort for Cohorts 2, 4, and 6. Assuming that the cohorts will be dosed based on safety reviews, it is intended that at least 3 Japanese patients will be enrolled in each dose cohort for Cohorts 3, 5, and 7. If the number of recruited Japanese patients per cohort is fewer than 3, then the randomization will continue. Japanese patients will continue to enroll with a 2:1 randomization ratio with the cohort. Details on the randomization plan will be described in the interactive web response system (IWRS).

This ratio is based on the enrolment rate of Study AACC.

Patients who are randomized but who do not complete the 12-week safety and PET assessment may be replaced.

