### 4.2. Data Analysis Plans

#### 4.2.1. General Considerations

Statistical analysis of this study will be the responsibility of Eli Lilly and Company or its designee.

Pharmacokinetic/PD analyses will be conducted on the full analysis set. This set includes all data from all randomized patients receiving at least 1 dose of the investigational product

according to the treatment the patients actually received. Safety analyses will be conducted for all enrolled patients, whether or not they complete all protocol requirements.

Summary statistics, data tabulations, and data graphs by ethnicity (Japanese and non-Japanese) will be provided as appropriate.

Additional exploratory analyses of the data will be conducted as deemed appropriate. Analyses will be fully detailed in the statistical analysis plan. Study results may be pooled with the results of other studies for population pharmacokinetic analysis purposes to avoid issues with posthoc analyses and incomplete disclosures of analyses.

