#### **4.2.5. Pharmacodynamic Analyses**

Pharmacodynamic and cognition measures as function of visit or time relative to first IV dose will be summarized and/or plotted as appropriate. As there will not be sufficient information to make informative comparisons on the Japanese population, all analyses will be conducted on the overall population unless otherwise specified. As the analyses are considered exploratory, changes to the planned analyses will not require a protocol amendment. The following sections provide details of the specific pharmacodynamic measure or cognitive measure.

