##### **4.2.5.1. Primary Objective of Amyvid PET Imaging Statistical Analyses**

Statistical assessment of the composite SUVr change from baseline will be analyzed by a mixed model repeated measure (MMRM). The response measurements are (1) SUVr change from baseline and (2) the percent change from baseline. Baseline is defined as the pre-dose SUVr obtained at screening visit 3 or prior to randomization. The change from baseline are computed from the SUVr obtained from the scheduled study visits at weeks 12, 24, 36, and 48. Patients have the option to have a PET image taken at early discontinuation. In those case, SUVr value will be mapped to the closest scheduled study visit at weeks 12, 24, 36, or 48. The planned analyses is an MMRM using an appropriate covariance structure with fixed effects of treatment doses (LY3002813 and placebo), study visit, and interaction between treatment and visit. A baseline covariate adjustment may be used. The primary comparison is between LY3002813 IV doses and placebo for change from baseline in composite SUVr or percent change in composite SUVr at last PET imaging visit. This analysis may be repeated for individual brain regions of SUVr if needed. A table of the LSmeans per dose group with associated p-value contrast to placebo will be constructed. A graphical summary of the LSmeans and a mean confidence interval on the y-axis and the study visit on the x-axis for each IV dose-group. Given the small sample size of n=6 patients per IV dose group, simplification of the mixed-effects model might be considered if the model fails to converge or other model fit diagnostics.

In addition to the MMRM analysis, a Bayesian posterior probability may be computed for each LY3002813 dose compared to placebo. For each dose, the credible interval will be computed for each dose relative to placebo. This analysis may be omitted if access to appropriate software such as SAS version 9.4 is not available.

Summary tables for SUVr values across the PET scan study visits for each IV dose group will include the n, mean, median, SD, minimum, maximum values. In addition, the number of patients within each IV dose group and study visit with post-dose composite SUVr values less than 1.2.

In addition to Amyvid PET scan SUVr analysis, an exploratory analysis of 18F-AV-1451 PET scan SUVr results will be conducted using an analysis of covariance (ANCOVA) model. The

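### Where the SAP's 2:1 rule for continuing Japanese enrollment is used, treatment becomes partially associated with ethnicity, and the SUVr and cognition MMRMs have no ethnicity term

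*SAP*

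**What the plan says.** **Allocation.** SAP 4.1 states that "the randomization ratio will be 6:2 in Cohorts 1, 2, and 3; randomization will progress with a 9:3 ratio in Cohorts 4 to 7", which is 3:1 in every cohort. It continues: "If the number of recruited Japanese patients per cohort is fewer than 3, then the randomization will continue", and "Japanese patients will continue to enroll with a 2:1 randomization ratio with the cohort". Details are left to the IWRS. The same section aims for at least two Japanese patients in Cohorts 2, 4 and 6 and at least three in Cohorts 3, 5 and 7. Protocol 9.2.1 describes one computer-generated sequence within each dose cohort and gives no ratio specific to Japanese patients.

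**Analysis.** The SUVr model in SAP 4.2.5.1 has "fixed effects of treatment doses (LY3002813 and placebo), study visit, and interaction between treatment and visit", and "A baseline covariate adjustment may be used". The cognition model in SAP 4.2.5.2 has the same form. SAP 4.2.5 says "all analyses will be conducted on the overall population unless otherwise specified". Ethnicity enters only descriptively in SAP 4.2.1: "Summary statistics, data tabulations, and data graphs by ethnicity (Japanese and non-Japanese) will be provided as appropriate". Protocol 11.2.3 permits demographic characteristics to be used in PD analyses but does not commit to it.

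**The concern.** When the probability of receiving placebo depends on a recorded group, randomisation makes the arms comparable within that group, not across the pooled sample. A pooled contrast that ignores the group is then unbiased only if the group does not predict the outcome, and nothing in the documents establishes that for SUVr change.

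The rule is not remote. It is triggered below three Japanese patients, while the SAP's target for Cohorts 2, 4 and 6 is two, so a cohort that just meets its target still triggers it. Protocol 7.1.7 and the lumbar-puncture footnote in Attachment 1 also foresee Japanese patients added after a cohort has filled.

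At stake is a small systematic shift in the primary drug-placebo contrast. Its direction is unknown, because it depends on the sign of any ethnic difference.

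**Working it through.** **1. The plan's own totals.** Completers: 3 × (6 + 2) + 4 × (9 + 3) = 72, of whom 54 are active and 18 placebo. This matches SAP 4.1. Japanese patients under protocol 7.1.7: 4 × 2 + 3 × 3 = 17, which matches the protocol.

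**2. Expected Japanese share by arm.** Assumptions: 2:1 means active to placebo; Japanese patients within the planned cohort size are allocated 3:1; the cohort is topped up to three. With k already in and 3 − k added:

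- Japanese on active = 0.75k + (2/3)(3 − k)
- Japanese on placebo = 0.25k + (1/3)(3 − k)
- arm totals = planned size plus the arm's share of the added patients

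| Cohort | Already in | Added | Active | Placebo | Gap (points) |
|---|---|---|---|---|---|
| 9:3 | 2 | 1 | 2.167/9.667 = 22.4% | 0.833/3.333 = 25.0% | 2.6 |
| 9:3 | 1 | 2 | 2.083/10.333 = 20.2% | 0.917/3.667 = 25.0% | 4.8 |
| 9:3 | 0 | 3 | 2/11 = 18.2% | 1/4 = 25.0% | 6.8 |
| 6:2 | 2 | 1 | 2.167/6.667 = 32.5% | 0.833/2.333 = 35.7% | 3.2 |
| 6:2 | 1 | 2 | 2.083/7.333 = 28.4% | 0.917/2.667 = 34.4% | 6.0 |
| 6:2 | 0 | 3 | 2/8 = 25.0% | 1/3 = 33.3% | 8.3 |

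Two study-wide cases bracket the same range. With 17 Japanese patients at 3:1 among the 72, plus 10 more at 2:1 (the SAP's limit on additional patients), the shares are 32.0% and 35.5%, a gap of 3.5. With 54:18 non-Japanese plus 21 Japanese patients all at 2:1 (14:7), a deliberately extreme case, they are 20.6% and 28.0%, a gap of 7.4.

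Upper bound: if every Japanese patient were at 2:1 and everyone else at 3:1, the odds ratio for being Japanese, active to placebo, is 2/3. The largest possible gap is then (√3 − √2)/(√3 + √2) = 0.101, or 10.1 points, reached at a Japanese share near 48%.

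**3. Bias.** Size of bias = gap × ethnic difference in SUVr percent change. The documents give no such difference. For an assumed 5 points, the top-up cases run from 0.026 × 5 = 0.13 to 0.083 × 5 = 0.42. For 2 points the largest is 0.17; for 10 points, 0.83.

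**4. Scale.** The protocol synopsis claims over 90% power for a 17% reduction with 6 per group but gives no SD or alpha, so that figure cannot be reproduced. Assuming two-sided 0.05, the largest SD compatible with it is 8.2 by the t distribution (9.1 by the normal). At SD 8.2, the unadjusted SE is:

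- 9:3 plus 2:1: 8.2 × √(1/11 + 1/4) = 4.79
- 6:2 plus 2:1: 8.2 × √(1/8 + 1/3) = 5.55
- study-wide, 54:18 plus 14:7: 8.2 × √(1/68 + 1/25) = 1.918

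The largest top-up bias at 5 points is 0.42/5.55 = 0.08 SE. At 10 points it is 0.83/5.55 = 0.15 SE. The extreme study-wide case at 10 points is 0.74/1.92 = 0.39 SE.

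**5. Type I error and cost of the term.** A single-visit linear-model simulation (40,000 replicates, no drug effect, SD 8.2) covered the three layouts in step 4. Without the term, rejection rates were 0.026 to 0.047 for ethnic differences of 5 to 10 points: below nominal, consistent with the ethnic variance sitting in the residual. With the term they were 0.049 to 0.051, and the expected bias is zero. The SE becomes SD/√(sum over ethnic groups of active × placebo/total):

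- 9:3 plus 2:1: 8.2/√(2.25 + 0.667) = 4.80
- 6:2 plus 2:1: 8.2/√(1.5 + 0.667) = 5.57
- study-wide: 8.2/√(13.5 + 4.667) = 1.924

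**6. Chance imbalance for comparison.** With three Japanese patients among 12 allocated 9:3 at random, the SD of the gap in Japanese share is √(3 × 0.75 × 0.25 × 9/11) × (1/9 + 1/3) = 0.30, or 30 points. That is well above the 3 to 8 points from the ratio.

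**The case against.** A reader might infer that treatment is confounded with ethnicity by design, and that placebo necessarily holds more Japanese patients. The documents do not support that. Both ethnic groups are randomised to both arms, so the association is partial and estimable. It arises only where the 2:1 rule is triggered and used; otherwise everyone is at 3:1. A gap of 8 to 10 points as the typical case would need nearly all Japanese patients to be at 2:1, or several more per cohort than the targets of two or three.

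The premise is also uncertain. The SAP sentence does not say what 2:1 refers to, and the IWRS specification is not in the documents. The SAP was approved in December 2015 and protocol amendment (f) in December 2017, so the rule may no longer operate. No passage shows that ethnicity predicts SUVr change. The bias is negligible against 17%, chance imbalance is larger, the PD analyses are declared exploratory, and the SAP anticipates simplifying its models at about six patients per dose rather than enlarging them.

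Most of this stands as a limit on size and certainty. It does not remove the point. Permission to use demographic variables is not a commitment to do so, and the larger chance imbalance is a further reason to include the term, since the term absorbs that as well.

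One further objection stands in full. An ethnicity term is not a site or scanner adjustment, because Japanese patients may be recruited outside Japan. A main effect also removes only a difference that is constant over visits.

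**Conclusion.** The concern holds as a minor one. Wherever the 2:1 rule is used, the pooled contrast is not fully protected by randomisation, because allocation then depends on a recorded group that the models omit. The expected excess of Japanese patients on placebo is about 3 to 8 percentage points under a top-up to three, and the bias about 0.1 to 0.4 SUVr percentage points for an assumed 5-point ethnic difference. There is no evidence of inflated type I error, and the bias could not by itself account for an effect near the 17% target.

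This rests on reading 2:1 as active to placebo, on the rule being applied as a top-up, and on assumed values for the ethnic difference, the SD and alpha. If the rule was never used, no design imbalance exists and the term serves only to handle chance imbalance.

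**What to change.** 1. Add Japanese/non-Japanese as a fixed effect in the SUVr MMRM (SAP 4.2.5.1) and the cognition MMRM (SAP 4.2.5.2), subject to the model simplification those sections already allow.
2. In SAP 4.1, state what the 2:1 ratio refers to, when it starts and stops, and whether it still applies; reconcile it with protocol 9.2.1.
3. Describe the term as adjustment for a group on which allocation depends, and claim no control of site or scanner differences.

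This is a free improvement. It uses one degree of freedom of about 64 (72 completers less seven dose groups and placebo), and the SE moves from 4.79 to 4.80 within a 9:3 cohort and from 1.918 to 1.924 study-wide. Japanese status is already needed for the planned summaries, and the SAP says that changes to these analyses need no protocol amendment.
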